## 15. Statistical analysis

The treated patients in this study will be compared to the placebo group. Measurements will include PCR test results, presence or absence of symptoms, and symptom severity. PCR results will be compared between the groups as positive or negative

In this study, the meaningful threshold will be calculated as mean change in clinical symptoms as recorded in the diary, from Day 1 through week 12. Each category in the diary will be assigned a number, 0 for None, 1 for Mild, 2 for Moderate and 3 for severe. Each category will be analyzed independently and they will be analyzed as a group. Ultimately, efficacy will be determined based upon reduction and/or progression of symptomatic days, reduction of symptom severity, as well as analysis of the subject's RT-PCR testing per protocol. These data will be compared to an existing database of de-identified Subject data.

The change of these measurements from the end to the baseline (post-pre) will be used as the primary outcome, for example,  $\mu_e = \mu_{e1} - \mu_{e0}$ , where  $\mu_{e1}$  and  $\mu_{e0}$  are the outcome of Subjects from the treatment group at the end and at baseline, respectively.

Categorical variables will be summarized by presenting the number (n) and percent (%) of subjects in each category. All Statistical tests for the analysis will be performed using the  $p < 0.05$  level of significance. All confidence intervals will be one-sided

Sample size was calculated as follows:

$$n = \frac{\log \beta}{\log \rho}$$

Where  $\beta = \text{the probability of a Type II error}$

$\rho = \text{the proportion of the population NOT affected}$

The proportion of the population affected by COVID-19 is 0.005 percent, thus 0.995 percent aren't affected

The probability of a type II error is 0.05

Thus:

$$n = \frac{\log 0.050}{\log 0.995}$$

$$n = 597.647$$

A sample size of 600 will be used

Additional details can be found in the Statistical Analysis Plan that will be developed prior to database lock.

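### Section 15 writes the primary outcome only as a raw change in the treatment group; it needs a stated contrast with placebo and, for the diary score, baseline adjustment

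*Combined protocol and SAP*

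**What the plan says.** Section 15 opens with the comparator: "The treated patients in this study will be compared to the placebo group". It then says of virology that "PCR results will be compared between the groups as positive or negative". Symptoms are scored from the diary: "Each category in the diary will be assigned a number, 0 for None, 1 for Mild, 2 for Moderate and 3 for severe". The categories are to be analysed singly and together, and the change in symptoms is taken from Day 1 to week 12. The section adds a second comparator whose role it does not explain: "These data will be compared to an existing database of de-identified Subject data".

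The primary outcome follows: "The change of these measurements from the end to the baseline (post-pre) will be used as the primary outcome". The only formula is mu_e = mu_e1 - mu_e0, where the two terms "are the outcome of Subjects from the treatment group at the end and at baseline, respectively". No matching placebo quantity, difference of changes, test, model or covariate is written. Further detail is left to a statistical analysis plan due before database lock; none appears in the text available.

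Three other places bear on this:
- **Section 6 (Schedule of Events)** marks the diary from Day 1 to Days 15-30 and at no later visit. It marks the first study swab on Day 3.
- **Section 2** gives the primary endpoint as days from diagnosis to recovery by RT-PCR.
- **The Synopsis** gives the same endpoint and adds symptomatic days and symptom severity under the primary objective.

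**The concern.** A primary outcome formula should show the quantity on which the efficacy claim rests. In a randomised placebo-controlled trial that is a difference between arms, and here the formula stops at one arm. An analyst working from it must infer the contrast, the model and the end time. The week 12 end time cannot be met from the diary, because no diary is scheduled after Day 30.

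The second issue is efficiency. If the missing step is filled in the obvious way, by comparing raw changes between arms, the result is valid but noisier than it need be. Subtracting the baseline in full adds its noise whenever the end score is only weakly related to it. That is plausible in an acute illness where many end scores are low. The schedule already includes a Day 1 diary, so adjusting for its score needs no new visit or measurement.

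**Working it through.** **The plan's own figure.** Section 15 computes n = log(0.05)/log(0.995) = 597.647, rounded to 600. This reproduces. The formula uses no outcome, effect size, standard deviation or arm, so 600 does not depend on how the primary outcome is analysed.

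**Inputs.** The documents give 600 completers, two arms, a 0.05 level and a 0-3 score. They give no standard deviation (SD), baseline-to-end correlation (rho), effect size or allocation ratio. They do not say whether tests are one- or two-sided, only "level of significance. All confidence intervals will be one-sided". I therefore assume rho from 0.2 to 0.7 and work in SD units. For power I also assume 1:1 allocation (300 per arm), a two-sided 0.05 test and a difference of 0.25 SD.

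**Variance ratio, equal SDs.** Per subject, in units of the outcome variance:
- raw change: 2(1 - rho)
- ANCOVA: 1 - rho²
- ratio: 2(1 - rho)/(1 - rho²) = 2/(1 + rho)

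The ratio does not depend on the allocation ratio. The number of ANCOVA subjects that matches 600 analysed by raw change is 600(1 + rho)/2. Power is approximately Phi(0.25/SE - 1.96), with SE = sqrt(2v/300) and v the variance above.

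| rho | change variance | ANCOVA variance | ratio | ANCOVA N matching 600 | power, change | power, ANCOVA |
|---|---|---|---|---|---|---|
| 0.2 | 1.60 | 0.96 | 1.67 | 360 | 68% | 88% |
| 0.3 | 1.40 | 0.91 | 1.54 | 390 | 74% | 89% |
| 0.5 | 1.00 | 0.75 | 1.33 | 450 | 87% | 94% |
| 0.7 | 0.60 | 0.51 | 1.18 | 510 | 98% | 99% |

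At rho = 0.9 the ratio is 2/1.9 = 1.05, so the loss almost disappears.

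**Unequal SDs.** Let k be the baseline SD divided by the end SD. The ratio becomes [(1 - rho²) + (k - rho)²]/(1 - rho²) = 1 + (k - rho)²/(1 - rho²). The added term is a square, so the ratio is never below 1, and it equals 1 only when k = rho. If end scores bunch near zero, k would exceed 1. With k = 2 as an illustration:
- rho = 0.3: (0.91 + 2.89)/0.91 = 4.18
- rho = 0.5: (0.75 + 2.25)/0.75 = 4.00
- rho = 0.7: (0.51 + 1.69)/0.51 = 4.31

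**Validity.** In 4,000 simulated trials with normal scores, 300 per arm, rho = 0.5, natural improvement of 1 SD and no drug effect, the between-arm change score rejected 5.7% of the time and ANCOVA 5.4%. The simulation standard error is sqrt(0.05 × 0.95/4000) = 0.34 percentage points, so both agree with 5%. The mean standard errors were 0.0816 and 0.0707, and the squared ratio is 1.33, as the formula predicts.

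**The case against.** A reader might infer that the plan credits natural recovery to the treatment. As arithmetic the hazard would be serious. A pre-post test in 300 treated subjects, with no drug effect and natural improvement of only 0.25 SD, would be significant 96% of the time at rho = 0.3 and 99% at rho = 0.5. But the documents do not describe that test. Section 15 begins with the placebo comparison, compares PCR results between groups, and offers the change as something that "will be used as the primary outcome, for example", which reads as an illustration of how change is computed in one arm. Under randomisation, a difference in changes between arms removes natural recovery. This objection stands in full. The undefined external database leaves some ambiguity, but it does not replace the placebo comparison.

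Four further objections have weight:
- **Efficiency, not error.** A between-arm change score is unbiased, and Section 15 names no test, so the unadjusted comparison is itself an inference. This stands, and it makes the point an improvement plus a clarification.
- **The later analysis plan could supply the contrast.** It could. Still, the contrast that defines efficacy is more than a detail, and the current text lacks it.
- **The equal-SD figures may not fit low end scores.** True. They are illustrations, and the direction holds for any SDs.
- **ANCOVA does not suit every measurement in Section 15.** True. PCR status is binary, days to RT-PCR recovery has no baseline value, and no study swab precedes Day 3. The remedy must be confined to the diary severity score.

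**Conclusion.** The point holds as a gap in specification and an avoidable loss of precision. The formula covers the treatment arm alone and omits the between-arm contrast; the symptom change is also taken to a week 12 for which no diary is scheduled. For the diary score, an unadjusted change has 1.67 to 1.18 times the ANCOVA variance for rho from 0.2 to 0.7. That range rests on assumed correlations, equal SDs and large samples. The true ratio cannot be read from the documents: it could be close to 1 or considerably larger, but not below 1. The power figures rest in addition on the assumed 0.25 SD effect, 1:1 allocation and two-sided testing. Bias from natural recovery is not established.

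**What to change.** In Section 15 and the analysis plan, for the diary symptom-severity score:
1. Write the contrast as (treated end - baseline) minus (placebo end - baseline), with the concurrent placebo arm as comparator, and say which diary score is meant.
2. Estimate it by ANCOVA of the end score on arm and pre-dose Day 1 score, in all randomised subjects. Using change as the dependent variable gives the same arm effect once baseline is in the model, so the change wording can be kept.
3. Name one end time within diary coverage, Day 30 at the latest. The choice matters: if scores are near zero in both arms by then, there may be little left to detect however efficient the model.
4. Say which Day 1 entry is the baseline. Section 6 marks a morning and evening diary on the first dosing day, whereas the Day 1 steps in Section 3 list only diary instruction and equipment readings.
5. State how missing diary entries are handled.

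Analyse PCR status and days to RT-PCR recovery by between-arm methods suited to binary and time-to-event data, not by this ANCOVA. Reconcile Section 15 with the RT-PCR recovery primary endpoint in Section 2 and the Synopsis, and state the role of the external database.

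The cost is wording plus clear labelling of a Day 1 entry already scheduled. The sample size of 600 does not change.

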## 2. Trial Objectives

Primary Study Objective	Study Endpoints
The rate of recovery of mild or moderate COVID-19 in Subjects using Quintuple Therapy	Number of Days Recovery from COVID-19 diagnosis to Recover via RT-PCR
Secondary Objectives	Study Endpoints
Assess the safety of Quintuple Therapy	Assess the symptom response to study therapy as measured by the survey in the EDC
	EKG response, oxygen saturation, and vital signs at baseline, 2 weeks, 1 month, and two months
Assess Tolerability of Quintuple Therapy	Assess Adverse Events and Serious Adverse Events due to Quintuple Therapy

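### The synopsis, Section 2 and Section 15 disagree on the primary outcome; Section 15 gives no success rule across three outcomes and makes every confidence interval one-sided without level or direction

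*Combined protocol and SAP*

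**What the plan says.** Section 15 states that "efficacy will be determined based upon reduction and/or progression of symptomatic days, reduction of symptom severity, as well as analysis of the" RT-PCR results. It then says: "The change of these measurements from the end to the baseline (post-pre) will be used as the primary outcome". The measurements are plural and none is singled out. For RT-PCR it says: "PCR results will be compared between the groups as positive or negative". Diary categories are to be analysed one by one and together; their number is not given.

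On error control the section has two sentences. One begins "All Statistical tests for the analysis will be performed using the" and sets p < 0.05 for every test, without saying whether tests are one- or two-sided. The other is "All confidence intervals will be one-sided", with no confidence level and no direction for the bound. No testing order, adjustment or rule for combining the three outcomes is given.

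Section 2 lists a single primary endpoint, "Number of Days Recovery from COVID-19 diagnosis to Recover via RT-PCR", and puts the symptom survey under secondary objectives. The synopsis table lists days to RT-PCR recovery and also symptomatic days and symptom severity under the primary heading.

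Section 15 also plans an external comparison: "These data will be compared to an existing database of de-identified Subject data". It closes by deferring detail: "Additional details can be found in the Statistical Analysis Plan that will be developed prior to database lock".

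**The concern.** A reader cannot tell from the protocol which result would make the trial positive. If symptoms improved but RT-PCR did not, two analysts following Section 15 could reach opposite conclusions from the same data. Whether the false-positive rate is inflated or the power is reduced depends on a rule that is not written down.

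The interval sentence is a second gap. The symptom outcome covers both improvement and worsening, yet a one-sided interval bounds only one direction. It cannot show both how much benefit and how much harm the data allow. Without a level or direction, it is also unclear which limit would be reported or whether it would agree with the test.

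**Working it through.** **1. The primary outcome, place by place.**

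| Place | Primary outcome | Form of the RT-PCR outcome |
|---|---|---|
| Section 2 | RT-PCR recovery only | days from diagnosis to recovery |
| Synopsis | RT-PCR recovery, plus symptomatic days and severity | days from diagnosis to recovery |
| Section 15 | change (post minus pre) in several measurements | positive or negative |

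These cannot all hold. A post-minus-pre change is also a poor fit for RT-PCR here: the first scheduled study swab is on Day 3 (Sections 3 and 6), and the inclusion criteria admit subjects on clinical diagnosis or a rapid antigen test.

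**2. The plan's own figure.** The sample size is n = log β / log ρ with β = 0.05 and ρ = 0.995. This gives ln(0.05)/ln(0.995) = 597.647, which reproduces and is rounded to 600. The formula contains no significance level, sidedness, effect size or number of outcomes, so it does not supply the missing rule.

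**3. If any one of three outcomes suffices.** Take three standard normal test statistics with common correlation r and no true effect (r is assumed; the documents give none). Count only results that favour treatment. With critical value c,

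P(any) = 1 − ∫ φ(u) Φ((c − √r·u)/√(1 − r))³ du, which is 1 − Φ(c)³ at r = 0.

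At r = 0 this is 1 − 0.975³ = 7.31% for two-sided 0.05 tests (c = 1.960) and 1 − 0.95³ = 14.26% for one-sided 0.05 tests (c = 1.645).

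| r | two-sided 0.05 (nominal 2.5%) | one-sided 0.05 (nominal 5%) |
|---|---|---|
| 0 | 7.31% | 14.26% |
| 0.3 | 6.83% | 13.03% |
| 0.5 | 6.27% | 11.84% |
| 0.7 | 5.46% | 10.27% |
| 0.9 | 4.18% | 7.95% |

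Separate diary-category tests would raise these if they also counted. Their number is not given, so no figure is offered.

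**4. If all three must succeed.** The false-benefit chance cannot exceed 2.5% (two-sided) or 5% (one-sided), the limits at r = 1. At r = 0.7 it is 0.44% and 1.15%. The cost is power. At an assumed 80% per outcome (two-sided 0.05), joint power is 0.8³ = 51.2% at r = 0, then 57.0%, 61.1%, 65.9% and 72.2% at r = 0.3, 0.5, 0.7 and 0.9.

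**5. Intervals.** At an assumed 95% level, a one-sided limit lies 1.645 standard errors from the estimate and a two-sided limit 1.960. For z between these values the two-sided p lies between 0.05 and 0.10. The one-sided interval would then exclude no effect while a two-sided test would not be significant.

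**6. Check of the remedies, under no effect.**
- Fixed order with RT-PCR as a gate: no claim is possible unless RT-PCR succeeds in favour of treatment, so false benefit is 2.5%.
- The same order without the gate: RT-PCR and symptomatic days are both tested regardless, giving 1 − 0.975² = 4.94% at r = 0 and 4.17% at r = 0.7. The gate must be written down.
- Holm across three co-equal outcomes (first step 0.05/3, c = 2.394): 2.48% at r = 0 and 1.96% at r = 0.7.

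**The case against.** The strongest reply is that Section 15 defers detail to a SAP due before database lock. In a double-blind trial that is ordinary practice, and that SAP may supply the rule. This stands as a limit on severity. It does not remove the point, because a SAP written to this protocol would inherit three conflicting primary definitions and an explicit one-sided instruction.

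Second, a list of outcomes joined as in Section 15 reads more naturally as a joint judgement than as a rule that any one suffices. Section 2 names one primary endpoint, and this is a Phase IIa study, where control of multiple testing is often lighter. A reader might infer that the plan inflates its false-positive rate to about 14%. The documents do not support that. They never say that one success is enough, and under an all-three rule there is no inflation. Zero correlation is also implausible for symptomatic days and severity, which come from the same diary, so 7.3% and 14.3% are upper ends.

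Third, one-sided intervals are legitimate when level, direction and matching test are stated. A reader might infer that tests and intervals will conflict. That follows only if the tests are two-sided, which is not stated. One-sided 0.05 tests with a 95% bound in the same direction would agree. Stating a level and direction would cure the ambiguity; the case for two-sided intervals is that they show both benefit and worsening.

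**Conclusion.** The point holds as a gap and an internal contradiction that should be fixed before unblinding, with medium confidence. Three current sections define the primary outcome incompatibly, Section 15 has no success rule, and its one-sided intervals have no level or direction.

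The size is conditional. If one outcome sufficed, false benefit would be 5.5-7.3% (two-sided tests) or 10.3-14.3% (one-sided tests) for correlations of 0.7 to 0, falling to 4.2% and 8.0% at 0.9. If all three are required, the price is joint power of 51-72% over correlations 0 to 0.9. The correlations, the 80% power and the 95% level are assumptions. The documents do not establish that error is inflated, only that they leave open whether it is.

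**What to change.** Before unblinding:

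1. Replace the one-sided sentence in Section 15 with: *All tests will be two-sided at 0.05, with two-sided 95% confidence intervals.*
2. Reconcile the synopsis, Section 2 and Section 15 to one primary outcome. If RT-PCR days to recovery is kept, bring Section 15's post-minus-pre and positive/negative wording into line with it, move the symptom outcomes to secondary in the synopsis, and state how subjects enrolled without a positive RT-PCR count.
3. Test symptomatic days, then total severity score, only if the RT-PCR primary is significant in favour of treatment, and stop at the first outcome that is not. The order of the two symptom outcomes is the sponsor's choice but must be fixed in advance. If all three are kept as co-equal primaries, use Holm across the three instead.
4. Label the per-category and external-database comparisons descriptive, and judge efficacy on the randomised placebo comparison.

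Cost: the primary analysis text must be rewritten, not just reworded. The limit that is now bounded moves from 1.645 to 1.960 standard errors (at an assumed 95%), and the other limit becomes finite. If one-sided 0.05 tests were intended, some power is lost: for example, from 92.2% to 86.5% at an assumed 300 per arm and standardised effect of 0.25. Under the fixed order, the symptom outcomes lose stand-alone claims if RT-PCR fails.

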
## Study Populations

### Inclusion Criteria

1. Informed consent provided electronically via the EDC, demonstrating that the subject understands the procedures required for the study and the purpose of the study
2. Male or female subjects 18 years of age and up
3. Subjects must agree to practice at least two highly effective methods of birth control for the duration of the study. This includes condoms with spermicide, oral birth control pills, contraceptive implants, intra-uterine devices, or diaphragms. At least one of these must be a barrier method. Subjects not of reproductive potential will be exempt (e.g. post-menopausal, surgically sterilized)
4. Diagnosis of COVID-19 by at least one of the following:
  - a. Physician diagnosis based on clinical presentation
  - b. Positive RT-PCR analysis
  - c. Positive rapid antigen test

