### Exclusion Criteria

1. Refusal to provide informed consent
2. Pregnant or breastfeeding women
3. Diarrhea prior to infection
4. Negative test for COVID-19 by RT-PCR or rapid antigen test at screening
5. Any comorbidities which, in the opinion of the investigator, constitute health risk for the subject
6. Any contraindications for treatment with hydroxychloroquine
  - a. Hypoglycemic
  - b. Known G6PD deficiency
  - c. Porphyria
  - d. Anemia
  - e. Neutropenia
  - f. Alcoholism
  - g. Myasthenia gravis
  - h. Skeletal muscle disorders
  - i. Maculopathy
  - j. Changes in visual field
  - k. Liver disease
  - l. Psoriasis
  - m. History of QT interval >500msec
  - n. History of torsades de pointes
7. Anemia from pyruvate kinase and G6PD deficiencies
8. Abnormal EKG with QT prolongation acquired or from birth
9. Allergies to 4-Aminoquinolines
10. History of jaundice or high fevers prior to developing COVID-19
11. Treatment with any of the medications listed in Appendix II
12. Treatment with any other drug not listed that affects the QT interval
13. Treatment with any anti-epileptics

ProgenaBiome, LLC Protocol PRG-044	21 July2020
Number of Subjects	
Subjects will be enrolled to ensure that at least 600 complete the study. It is anticipated that screening of 1200 Subjects will be required to achieve this.	
Specimen Requirements:	
NP swabs (synthetic swab on plastic shaft) placed into 2-3mL of viral transport media. 1 mL of blood in an EDTA and 2 mL of serum in two serum separator tubes spun down	
Study Duration	
Screening of 1200 Subjects and enrollment of 600 Subjects is expected to take 3 months	

Primary Study Objective	Study Endpoints
The rate of recovery from COVID-19 in Subjects using Quintuple Therapy	Number of days from COVID-19 diagnosis to recovery via RT-PCR
Reduction or Progression of Symptomatic Days	Reduction and/or progression of symptomatic days, reduction of symptom severity
Secondary Objectives	Study Endpoints
Assess the safety and Tolerability of Quintuple Therapy	Assess the symptom response to study therapy as measured by the survey in the EDC
	EKG response, oxygen saturation, and vital signs at baseline, 2 weeks, 1 month, and two months
	Assess Adverse Events and Serious Adverse Events due to Quintuple Therapy

- a. Adverse event monitoring will be conducted for 12 weeks
- b. Serious adverse event monitoring will be conducted for 12 weeks

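### The sample size of 600 answers a prevalence-sampling question, so the stated 5% type II error belongs to no comparison between the arms

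*Combined protocol and SAP*

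**What the plan says.** Section 15 (Statistical analysis) gives n = log(beta)/log(rho), where beta is called the type II error probability and rho is the unaffected proportion of the population. The inputs are stated as "The proportion of the population affected by COVID-19 is 0.005 percent, thus 0.995 percent" not affected, and "The probability of a type II error is 0.05". The result is 597.647, followed by "A sample size of 600 will be used". No other section gives a power calculation. Section 15 defers further detail to an SAP to be written before database lock.

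The surrounding text describes a different problem:

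- **Population.** The inclusion criteria require "Diagnosis of COVID-19 by at least one of the following" (clinical diagnosis, RT-PCR or rapid antigen test), and a negative RT-PCR at screening excludes.
- **Comparison.** Section 15 compares the treated group with the placebo group on PCR results and symptoms. Tests are at the 0.05 level with sidedness not stated, although "All confidence intervals will be one-sided".
- **Primary endpoint.** The synopsis lists two under its primary heading: "Number of days from COVID-19 diagnosis to recovery via RT-PCR" and "Reduction and/or progression of symptomatic days, reduction of symptom severity". Section 2 lists only the first of these. Section 15 says "The change of these measurements from the end to the baseline (post-pre) will be used as the primary outcome".
- **Status of the 600.** Under Number of Subjects the synopsis asks for no fewer than 600 completers. Under Study Duration it plans to enrol 600. No dropout rate is given.

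**The concern.** A sample-size calculation for a two-arm trial needs the difference to be detected, the variability or control-arm event rate, the significance level and the allocation. The formula in Section 15 has none of these. Its only inputs are an error probability and the prevalence of infection in what appears to be the general population (the protocol says only the population). Prevalence plays no part in a trial of people who already have the diagnosis.

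A stated type II error of 5% reads as 95% power. If no planned comparison has been shown to have that power, a null result could be presented as firm evidence of no effect without support. The ethics board and later readers would also have no valid rationale for the size of the trial.

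**Working it through.** **1. Reproduce the plan's figure.** Inputs from Section 15: beta = 0.05, rho = 0.995.

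n = ln(0.05)/ln(0.995) = (−2.99573)/(−0.00501254) = 597.647, which matches. The arithmetic is right.

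**2. What the formula solves.** Rearranged, it is rho^n = beta. If each person drawn is unaffected with probability rho, rho^n is the chance that all n are unaffected. At n = 600:

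- chance of no affected person: 0.995^600 = 0.0494
- chance of at least one: 1 − 0.0494 = 0.9506

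So the 0.05 is the chance of drawing no cases. It is not the chance of missing a treatment difference.

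**3. The percent label.** Read literally, 0.005 percent is a proportion of 0.00005, and n = ln(0.05)/ln(0.99995) = 59,913. The calculation therefore used 0.005 and 0.995 as proportions (0.5% and 99.5%). This is a labelling slip. Correcting it does not repair the method.

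**4. What 600 gives for a comparison between arms (illustration).** The documents give no control rate, effect, standard deviation, allocation ratio or test sidedness. Assumptions: 1:1 allocation, 300 per arm, alpha 0.05, PCR-negative proportion as endpoint, control rates of 50% to 80%, a rise of 10 points. The formula is

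power = Φ{ [d − z_α·√(2p̄(1−p̄)/n)] / √([p1(1−p1) + p2(1−p2)]/n) }

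with d = p2 − p1, p̄ = (p1 + p2)/2, and z_α = 1.960 two-sided or 1.645 one-sided.

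Example, 50% against 60%, two-sided: √(2 × 0.55 × 0.45/300) = 0.04062 and √((0.25 + 0.24)/300) = 0.04041. Then (0.10 − 1.960 × 0.04062)/0.04041 = 0.504, and Φ(0.504) = 69.3%.

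| Control rate | Two-sided, 300/arm | One-sided, 300/arm | Two-sided, 255/arm | One-sided, 255/arm |
|---|---|---|---|---|
| 50% | 69.3% | 79.4% | 62.2% | 73.5% |
| 60% | 72.9% | 82.3% | 65.9% | 76.6% |
| 70% | 80.9% | 88.3% | 74.3% | 83.4% |
| 80% | 93.1% | 96.4% | 88.8% | 93.7% |

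The 255 per arm is 600 enrolled with 15% lost (assumed): 600 × 0.85/2. A simulation with 400,000 runs per cell at 300 per arm gave 70.4/73.0/81.2/93.5% two-sided and 79.1/82.1/88.5/96.7% one-sided, which agrees.

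**5. Smallest detectable rise at 300 per arm, in percentage points.** Same formula, solved for d.

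| Power | Two-sided, control 50% | Two-sided, control 80% | One-sided, control 50% | One-sided, control 80% |
|---|---|---|---|---|
| 80% | 11.3 | 8.3 | 10.1 | 7.5 |
| 90% | 13.1 | 9.5 | 11.8 | 8.7 |
| 95% | 14.5 | 10.4 | 13.3 | 9.6 |

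**6. Other endpoint types at 95% power.**

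- Mean change: standardised difference = (z_α + 1.645) × √(2/300) = 0.294 two-sided, 0.269 one-sided.
- Time to recovery, assuming all 600 recover: hazard ratio = exp[(z_α + 1.645)/√150] = 1.34 two-sided, 1.31 one-sided. Two-sided power is 21% at a hazard ratio of 1.1 and above 99% at 1.5.

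**7. Enrolled or completed.** The two synopsis statements agree only if nobody is lost. With loss of 5% to 20% (assumed), 600 enrolled leaves 600 × 0.95 = 570 to 600 × 0.80 = 480 evaluable. To have 600 completers, 600/0.95 = 632 to 600/0.80 = 750 must be enrolled.

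**The case against.** The strongest reply is that 600 may well be enough. Section 1 cites 93% RT-PCR negativity by day 8 in an uncontrolled treated cohort. If control were 83% (assumed), the formula in step 4 gives about 97% power two-sided and 98% one-sided at 300 per arm, above the table's range. That is fair. The illustration shows no shortfall, and its control rates and 10-point effect are assumptions. But the 93% is not a control rate, the protocol does not use it for sizing, and an adequate number reached by chance does not make the stated error rate true.

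It can also be said that the protocol never claims 95% power in words, that this is a single-centre Phase IIa study, and that an SAP is still to come. The first two soften the consequence: a misread null result is a risk rather than a certainty. The SAP does not help, because the sample size and its error rate are already fixed in Section 15.

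Finally, the enrolment wording may be no more than a loose timeline statement, and the choice of primary endpoint is a separate question. Neither is needed to show that the formula is wrong. Both matter for the repair, because a valid power statement needs one endpoint and one evaluable number.

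**Conclusion.** The concern holds and must be corrected. The error is in the choice of formula. The figure of 597.647 is correctly computed, but it is the number of draws for a 95% chance of finding at least one case at 0.5% prevalence. The 5% type II error applies to no comparison in this trial, and the documents give no other basis for 600.

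This does not show that 600 is too few. Under the stated assumptions, power for a comparison between arms runs from about 21% to over 99% according to the effect assumed, so no fixed error rate can be attached to 600 until an endpoint and a difference are named. The reading of the population as the general population is an inference, but a 0.5% infection rate cannot describe a trial of diagnosed patients.

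**What to change.** - Delete the formula, the prevalence input and the 0.05 type II error statement from Section 15.
- Name one primary endpoint and use it in the synopsis, Section 2 and Section 15.
- State the difference that the planned size can detect on that endpoint at 80% and 90% power. Show the control-arm assumption as a range, and give alpha, sidedness and allocation ratio.
- Reconcile the completer target with the enrolment figure in the synopsis, and base the power statement on the resulting evaluable number.

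**Cost.** Restating the power is wording only, and the implied 95% becomes less favourable. Naming the primary endpoint is a design decision for the sponsor and carries through to the objectives and analysis text. Reading 600 as enrolled adds no patients but leaves 480 to 570 evaluable at 20% to 5% loss (assumed). Keeping 600 completers means enrolling 32 to 150 more than 600 over the same range of loss.
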